To compare the incidence of mechanical ventilation or death in subjects with severe COVID-19 given placebo or oral duvelisib.	The primary end-point is a composite endpoint of mechanical ventilation or death within 4 weeks of randomization.
Secondary	
Secondary Objectives are to compare the duvelisib cohort to the placebo cohort with respect to:
 
1) Days to recovery as assessed by ACTT endpoints as the time to recovery (Day 1 through Day 29) to satisfy a score of ≥ 5 from the following eight categories from the NIAID ordinal scale. The scale is as follows: 1. Death; 2. Hospitalized, on invasive mechanical ventilation or extracorporeal membrane oxygenation (ECMO); 3. Hospitalized, on non-invasive ventilation or high flow oxygen devices; 4. Hospitalized, requiring supplemental oxygen; 5. Hospitalized, not requiring supplemental oxygen - requiring ongoing medical care (COVID-19 related or otherwise); 6. Hospitalized, not requiring supplemental oxygen - no longer requires ongoing medical care; 7. Not hospitalized, limitation on activities and/or requiring home oxygen; 8. Not hospitalized, no limitations on activities.2) Duration of hospitalization3) Death within 29 days of randomization4) ICU transfer within 29 days of randomization5) ECOG performance status at day 15 and 29 of randomization6) Incidence of grade III-V adverse events or SAEs (as defined by CTCAE version 5)7) Documented secondary bacterial or viral infection within 29 days of randomization.8) Mean frequencies of Th1 and Th17 T cells in blood mononuclear cells at 1, 2 and 4 weeks9) Mean levels of inflammatory serum biomarkers at 1, 2 and 4 weeks10) Gene expression profiles of T cells at 1, 2 and 4 weeks

OBJECTIVES	ENDPOINTS
11) Median titers of IgG antibodies to SARS-CoV-2 at 4 weeks 12) Survival at day 50-60 after randomization	

3. Background

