3.1 Study Rationale

COVID-19 patients have a poor prognosis, especially in the setting of co-morbidities, the presence of inflammatory serum markers, and declining oxygenation levels, with reported frequency of ICU transfer up to 50% and death of 25% (1, 2). Serum inflammatory markers in patients with severe COVID-19 including those that require ICU care and respiratory support with mechanical ventilation are reported to be higher than in patients with less severe disease (1), and COVID-19 patients develop a pattern of interstitial pulmonary infiltrates (3, 4) that are similar to those seen among patients that develop auto-immune pneumonitis in the setting of treatment with monoclonal antibodies that block immune check-point signaling (5). Taken together, these clinical and laboratory observations have led to the hypothesis that COVID-19 leads to hyper-immune activation, also termed “cytokine storm”(6). Immunomodulatory clinical interventions that are currently being evaluated included antibodies that block IL6 signaling (22 trials), IL1 signaling (5 trials), and tyrosine kinase inhibitors to Bruton’s tyrosine kinase (BTK) (7), Janus2 Kinase (JAK) (2 trials). The common theme in these studies is the hypothesis that intra-cellular signaling pathways of immune cells are hyper-activated, that immune hyperactivation contributes to alveolar damage and impairments in gas exchange, and that clinical interventions to block intra-cellular tyrosine kinase-mediated signaling pathways activated during COVID-19 will prevent or reverse the alveolar damage and hypoxemia that characterizes this disease. Recently, clinical data from CLL patients treated with duvelisib, a dual PI3K gamma/delta inhibitor, indicate lower levels of serum inflammatory markers during PI3Ki exposure (8). Addition of PI3K inhibitors, including duvelisib, during *ex vivo* expansion of T cells stimulated with anti CD3/CD28 beads indicates PI3K-inhibition appears to block differentiation of T cells from naïve/central memory to effector phenotypes, increases frequencies of CD8+ T cells, and improves *in vivo* persistence and anti-tumor activity when PI3Ki-expanded T cells are reinfused *in vivo* (9). Paradoxically, continuous exposure to duvelisib over a period of months has been associated with both opportunistic infections (10, 11) as well as auto-immune toxicities (12, 13), supporting the idea that duvelisib is an immunomodulatory drug, and indicating that short-term exposure to PI3Ki may have different immunological consequences than long-term exposure.

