It is anticipated that participants may be treated with antibacterial agents, either for concomitant infection, or bacterial superinfection, anti-coagulants, and passive antibody treatment (immune plasma or purified antibodies reactive to SARS-CoV-2 epitopes). The final decision for antibiotics (need, drug[s] and dose) and other medications will be made by the treating physician (except as noted below under Prohibited Medications). Concomitant use of medications that are sensitive CYP450 substrates (Appendix C) are prohibited, unless

Protocol Title: Duvelisib Ameliorates Manifestations of Pneumonia in Established Novel Coronavirus Infection (DAMPEN-CI)

absolutely necessary. If concomitant use of a medication which is a CYP450 substrates is required, then adverse events (AEs) should be monitored every 2 days.

Pneumocystis jirovecii pneumonia (PJP) and CMV prophylaxis.

Since duvelisib or placebo exposure is only 14 days, the risk of developing PJP or CMV viremia in this study is low, and specific antimicrobial prophylaxis with Bactrim (PJP) and valganciclovir (CMV) for a 14 period would be of limited clinical benefit given the short time of exposure to duvelisib, and prophylaxis with Bactrim and/or valganciclovir could lead to a higher incidence of blood cytopenia which might trigger stopping the study drug. Given the short term exposure to duvelisib, no PJP or CMV prophylaxis is mandated by the protocol, although treating physician may prescribe such medications if deemed to be in the interests of the subject.

Prohibited Medications and Food

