5.6 Description of Data Collection

Definition of Study Assessments

All patients will be closely monitored for safety and tolerability throughout the study. Patients will continue dosing until they experience intolerable AE's, discharge from hospital, patient withdrawal or termination of the study. Subjects may be discontinued from study treatment in the following situations: 1) subject has decided to withdrawal from the study, 2) Intolerable adverse events, 3) mechanical ventilation (e.g. intubation, high-flow O₂ Bi-PAP or AIRVO) or death, 4) pregnancy, or 5) severe noncompliance. The schedule of activities is listed in section C.

Medical History

Medical history and demographics will be collected at screening. Medical history will include other significant co-morbidities, previous surgeries, history of hypertension, chronic obstructive lung disease, asthma, diabetes, cancer, previous chemotherapy and outcomes, prior immunosuppressive drug therapy including

Protocol Title: Duvelisib Ameliorates Manifestations of Pneumonia in Established Novel Coronavirus Infection (DAMPEN-CI)

steroids, use of tobacco, alcohol and recreational drugs and any known toxin exposure. Demographics data will include age, sex and self-identified race/ethnicity.

Performance Status

The ECOG performance status will be assessed at screening and on days 1 [baseline, prior to study drug], 8, 15, and 29.

Physical Exam

Physical exam will include focused examination of body systems, including assessment of ECOG performance status, weight, heart, lungs, abdomen, skin and nervous system. A targeted physical exam will be performed on screening and on days 1 [baseline, prior to study drug], 8, 15, and 29.

Clinical Assessments

Vital signs will be recorded daily including maximal and minimal blood pressure, heart rate, temperature, oxygen saturation. Daily weights will be recorded. The maximum level of supplemental oxygen delivered in each 24-hour period will be recorded. Results from imaging studies of the lung ordered as part of the standard-of-care management of COVID-19 patients will be extracted from the electronic medical record and entered into case report forms. Positive results from microbiological tests of blood, sputum, and bronchial lavage ordered as part of the standard-of-care management of COVID-19 patients will be extracted from the electronic medical record and entered into case report forms.

Clinical Laboratory Data

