Immune related toxicities are the most common non-hematological adverse event (AE) with duvelisib. Elevated AST/ALT and diarrhea are the most common non-hematological AEs. The rates of diarrhea ranged from 42-51% in clinical trials with a median onset of 2.2-4 months (28, 8). The median time of onset for AST/ALT elevation was 1.2 months and occurred in 39% of patients in one phase I clinical trial (28). Other non-hematological AE's that have been reported include:

- 1) risk of infection (reported in 61-69% of patients with upper respiratory tract infections and pneumonia being the most common infections (8, 29).) There have also been reports of *Pneumocystis jirovecii* with the use of duvelisib.
- 2) risk of pneumonitis,
- 3) risk of intestinal infection and colitis,
- 4) risk of severe skin reactions (maculopapular rash)
- 5) Neutropenia (the most common hematological AE, occurring in 29%-39% of patients in clinical trials)
- 6) pyrexia

Other Risks:

Risk of Phlebotomy- The primary risks of phlebotomy include local discomfort, occasional bleeding or bruising of the skin at the site of needle puncture, and rarely hematoma, infection, or fainting. At the time of enrollment and during study visits, each participant will be asked about participation in other research studies to ensure that blood draws do not exceed the following amounts for all research protocols combined: 10.5 mL/kg or 550 mL, whichever is smaller, over any 8-week period for adults, and no more than 5 mL/kg may in a single day (no more than 9.5 mL/kg may be drawn over any 8-week period) for persons under the age of 18.

Risk of Nasopharyngeal Swab- The primary risk of a nasal swab is local discomfort. Rarely, there can be local bleeding from the nasal mucosa, which is controlled with local measures such as pressure or packing with gauze.

Risk of Oropharyngeal Swab- The primary risk of an oropharyngeal swab is local discomfort. This swab can stimulate the gag reflex, and very rarely vomiting.

Risk of Endotracheal Aspirate- The primary risk of endotracheal aspirate is cough, and rarely can cause a small amount of bleeding.

Data security- Subjects will be asked to provide personal health information (PHI). All attempts will be made to keep this PHI confidential within the limits of the law. However, there is a chance that unauthorized persons will

Protocol Title: Duvelisib Ameliorates Manifestations of Pneumonia in Established Novel Coronavirus Infection (DAMPEN-CI)

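### The infection endpoint counts only bacterial or viral infection, so Pneumocystis and other fungal infections drop out of the only dedicated infection comparison, and stool-only diagnoses have no listed route to the CRF

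*Combined protocol and SAP*

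**What the plan says.** The infection endpoint appears three times with the same wording: among the objectives and among the endpoints in the Section 1.1 synopsis, and in the Section 2 table. It reads "Documented secondary bacterial or viral infection within 29 days of randomization". Under Section 15.1 (Analysis of Secondary Endpoints), categorical endpoints such as this one are summarised by arm and compared with Fisher's exact test.

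The only text on abstracting on-study microbiology is in Section 5.6 (Clinical Assessments). It covers "Positive results from microbiological tests of blood, sputum, and bronchial lavage ordered as part of the standard-of-care management of COVID-19 patients".

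On the drug's infection risks, Section 13 states "There have also been reports of *Pneumocystis jirovecii* with the use of duvelisib" and also lists "risk of intestinal infection and colitis". Section 3.1 says that "continuous exposure to duvelisib over a period of months has been associated with both opportunistic infections". Section 5.1 gives a lower risk of opportunistic infection as one reason for limiting exposure to 14 days. Section 5.4 says that "the risk of developing PJP or CMV viremia in this study is low" and that "no PJP or CMV prophylaxis is mandated by the protocol". It adds that prophylactic drugs could themselves cause cytopenias, and that the treating physician may still prescribe them.

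**The concern.** An infection endpoint in a trial of an immunomodulatory drug should be able to count the infections that the protocol itself associates with that drug. This one leaves out a whole class of organism, and the class includes the one pathogen that Section 13 names. Section 5.4 makes a paired statement about PJP and CMV. The endpoint can count CMV, which is viral, but not PJP, so half of that statement goes unobserved in the infection comparison.

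If duvelisib caused an excess of fungal infection, this endpoint would not show it. The published infection result could then be read as reassurance on a question that the endpoint never asked. The stool gap works differently. Those events belong to the endpoint, but whether they are counted depends on how each site understands a documented infection, a term that the plan does not define.

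**Working it through.** The plan states no infection rate and no power for this endpoint, so there is no figure to reproduce. The check sets the endpoint wording (Sections 1.1 and 2) against the abstraction list (Section 5.6).

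| Infection and how it is proven | Within the endpoint wording? | Listed route to the CRF? | Counted? |
|---|---|---|---|
| Pneumocystis or other fungus, sputum or lavage | No | Yes | No |
| Fungus, blood | No | Yes | No |
| CMV, blood | Yes | Yes | Yes |
| Bacterial or viral gut infection with a positive blood result | Yes | Yes | Yes |
| Bacterial or viral gut infection, stool only | Yes | No | Uncertain |
| Fungal gut infection, stool only | No | No | No |

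For Pneumocystis the cause is the definition and not the data collection. The result reaches the CRF and the endpoint wording then discards it. For stool-only bacterial or viral infection the cause is the abstraction list.

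**Is there a backstop elsewhere?**
- Section 15.1 (Stopping Rule for Safety; Analysis of Safety Data) names death or mechanical ventilation, transaminase elevation and neutropenia. It has no infection term.
- Section 16.2 (Study-Specific AE/SAE Reporting) restricts grading and reporting to a set of laboratory tests plus diarrhea, bradycardia, symptoms leading to ICU admission and ventilation, repeat hospitalization, and death. Infection is not on the list. Diarrhea would appear without its infectious cause. Severe PJP could appear only as ICU admission, ventilation or death, which is hard to tell from progression of COVID-19.
- Section 16.1 and Section 16.2 (Documenting Adverse Events) call for all AEs to be recorded. That conflicts with the restricted list, so it cannot be relied on to close the gap.

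**Illustrative size.** The documents give no fungal rate. Assume a true duvelisib-arm rate between 2.5% and 10%, with 40 patients per arm:
- 0.025 × 40 = 1 patient
- 0.10 × 40 = 4 patients

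Under the present wording the endpoint counts 0 of these at any rate.

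**What a corrected endpoint could show.** Two figures mark its limits.
- With 0 of 40 events, the one-sided 95% upper bound is 1 − 0.05^(1/40) ≈ 7.2%.
- For 4/40 against 0/40, the two-sided Fisher p-value is 2 × C(40,4)/C(80,4) = 2 × 91,390/1,581,580 ≈ 0.12.

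The gain is therefore a complete descriptive count. It is not a powered test.

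**The case against.** The strongest reply is that little is lost. Respiratory fungal results are on the CRF whatever the organism, so they could be tabulated at the end. Grade III-V AEs and SAEs are compared by arm as a separate secondary endpoint, the IDMC reviews Grade 3 and 4 events by arm monthly (Section 15.1), and cumulative SAEs are monitored monthly (Section 16.3). Section 3.1 ties opportunistic infection to months of exposure, whereas this trial gives 14 days. The endpoint is one of about a dozen mainly descriptive secondary endpoints and drives no decision rule.

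Most of this stands, and it limits the importance of the point. It does not rescue the wording. Data that could be tabulated are not the same as data that the pre-specified comparison counts, and the AE route is unclear for the reasons given in the check. A low expected count is no reason to define the count as zero.

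A reader might go further in three ways that the documents do not support:
- *That intestinal infection cannot register at all.* Bacterial and viral gut infections fit the endpoint, a blood-positive case has a listed route, and nothing restricts the endpoint to the Section 5.6 specimens. The defect is confined to possible under-capture of stool-only diagnoses.
- *That the 61-69% infection figure in Section 13 measures what is missed.* That figure is overall infection in earlier duvelisib trials, where upper respiratory infection and pneumonia were the most common types. It is not a fungal or stool-only rate.
- *That the present wording is what stops the trial testing whether PJP risk is low.* With 40 patients per arm the trial could not settle that under either wording, as the two limits in the check show.

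**Conclusion.** The point holds in two parts of unequal strength. The exclusion of Pneumocystis and other fungal infection is certain, because it follows from wording used identically in three places. The under-capture of infection shown only in stool is likely but not certain, because the plan neither defines a documented infection nor says that the Section 5.6 list is exhaustive.

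The effect on the final count is unknown. The 1 to 4 patients of 40 rests wholly on the assumed 2.5% to 10%, and with 14 days of exposure the real number may be nil. A bias toward no harm would arise only if the uncounted infections were more frequent on duvelisib. The documents give no rate by which to judge that. The primary analysis and the interim rules are unaffected. The change is still worth making, because it alters what the stated endpoint counts, concerns an infection that the protocol names as reported with the drug, and costs almost nothing. It concerns measurement only and takes no position on prophylaxis.

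**What to change.** 1. In Sections 1.1 (objectives and endpoints) and 2, add fungal infection to the bacterial and viral categories, state that Pneumocystis is included, and keep the 29-day window.
2. In Section 5.6, abstract positive standard-of-care microbiology from any specimen, including stool, and say what makes an infection documented for this endpoint.
3. Tabulate opportunistic infections by arm as a descriptive subset of the endpoint, and give the table to the IDMC.
4. Reconcile the restricted list in Section 16.2 (Study-Specific AE/SAE Reporting) with the text in Sections 16.1 and 16.2 that calls for all AEs to be recorded, so that it is clear whether an infection is reported as such.

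The cost is a few words in the endpoint and the CRF and slightly more chart abstraction. The results are already in the medical record, and no new test or blood draw is needed.

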3.1 Study Rationale

COVID-19 patients have a poor prognosis, especially in the setting of co-morbidities, the presence of inflammatory serum markers, and declining oxygenation levels, with reported frequency of ICU transfer up to 50% and death of 25% (1, 2). Serum inflammatory markers in patients with severe COVID-19 including those that require ICU care and respiratory support with mechanical ventilation are reported to be higher than in patients with less severe disease (1), and COVID-19 patients develop a pattern of interstitial pulmonary infiltrates (3, 4) that are similar to those seen among patients that develop auto-immune pneumonitis in the setting of treatment with monoclonal antibodies that block immune check-point signaling (5). Taken together, these clinical and laboratory observations have led to the hypothesis that COVID-19 leads to hyper-immune activation, also termed “cytokine storm”(6). Immunomodulatory clinical interventions that are currently being evaluated included antibodies that block IL6 signaling (22 trials), IL1 signaling (5 trials), and tyrosine kinase inhibitors to Bruton’s tyrosine kinase (BTK) (7), Janus2 Kinase (JAK) (2 trials). The common theme in these studies is the hypothesis that intra-cellular signaling pathways of immune cells are hyper-activated, that immune hyperactivation contributes to alveolar damage and impairments in gas exchange, and that clinical interventions to block intra-cellular tyrosine kinase-mediated signaling pathways activated during COVID-19 will prevent or reverse the alveolar damage and hypoxemia that characterizes this disease. Recently, clinical data from CLL patients treated with duvelisib, a dual PI3K gamma/delta inhibitor, indicate lower levels of serum inflammatory markers during PI3Ki exposure (8). Addition of PI3K inhibitors, including duvelisib, during *ex vivo* expansion of T cells stimulated with anti CD3/CD28 beads indicates PI3K-inhibition appears to block differentiation of T cells from naïve/central memory to effector phenotypes, increases frequencies of CD8+ T cells, and improves *in vivo* persistence and anti-tumor activity when PI3Ki-expanded T cells are reinfused *in vivo* (9). Paradoxically, continuous exposure to duvelisib over a period of months has been associated with both opportunistic infections (10, 11) as well as auto-immune toxicities (12, 13), supporting the idea that duvelisib is an immunomodulatory drug, and indicating that short-term exposure to PI3Ki may have different immunological consequences than long-term exposure.

This study will examine if a 2-week exposure to duvelisib in patients with severe COVID-19, will favorably change their immune profile, decreasing alveolar inflammation and damage, and decrease the incidence of patients who require mechanical ventilation or who die.

3.2 SARS-CoV-2 and COVID-19

Severe acute respiratory syndrome coronavirus-2 (SARS-CoV-2) is a novel emerging pathogen that results in an illness called Coronavirus Disease 2019 (COVID-19). COVID-19 is an acute flu-like illness characterized by fever, dry cough and shortness of breath. In approximately 80-85% of individuals these symptoms will be mild to moderate, whereas in certain patient subgroups, such as the elderly and those with chronic cardiovascular disease, the illness may be severe, resulting in hypoxic respiratory failure and death (1, 14). Prior to the development and after resolution of symptomatic disease, patients shed virus in mucosal surfaces, which facilitates spread of the disease. SARS-CoV-2 has a basic reproductive number of >2, meaning that the disease has the potential to expand at exponential rates. The outbreak started initially as 4 cases of severe pneumonia in Wuhan, China, but on March 11th, 2020, with over 118,000 cases spread across over 110 countries, the World

Protocol Title: Duvelisib Ameliorates Manifestations of Pneumonia in Established Novel Coronavirus Infection (DAMPEN-CI)

Health Organization (WHO) declared Covid-19 a pandemic. As of April 19, 2020, according to the Center for Disease Control and Prevention, there were over 690,000 confirmed cases and 35,000 deaths in the US due to this disease (<https://www.cdc.gov/coronavirus/2019-ncov/casesupdates/cases-in-us.html>), and experts predict that the number of individuals needing hospitalization and respiratory support may outpace existing capacity. Agents under investigation for treatment of COVID-19 include, but are not limited to, remdesivir, a nucleotide analogue, chloroquine and hydroxychloroquine, IL-6 blockers and lopinavir/ritonavir, as reviewed (15).

